Assuming assumptions are valid, an increasing exponential regression model with random intercept will be fitted with Time of Four Ratio versus Time, stratified by the natural log of the five dose levels (modeled below). This translates to a slow response initially followed by a more rapid response later. The random intercept will allow for different initial TOFR values.

Page 9 of 30 Version: 3 (10/14/2024)

$$TOFR = \frac{1}{B}e^{(A+time)/B} + TOFR_{initial} + C * \ln(dose)$$

"Success" will be defined as TOFR of ≥0.9 within 5 minutes for 95% of patients, following the model estimate, adjusting for the 95% confidence intervals of the estimates, based on initial TOF ratios, which may be grouped as needed. A secondary analysis will be conducted by TOFC to determine optimal dose at each TOFC level, and if TOFC correlates strongly with TOFR.

8. Data and/or Specimen Banking

N/A

9. Sharing of Results with Participants

N/A

10. Study Timelines

All subjects are anticipated to participate in the study from the start of their surgery to the time of their discharge from the PACU, which should be on the same day. It is expected that 1 year would be required to enroll all study subjects, and for the study to be completed by July 2023.

11. Inclusion and Exclusion Criteria

Individuals will be screened for eligibility at the anesthesia pre-admission clinic.

Inclusion criteria:

- Patients aged 18 years and above who will
- Undergo an elective surgery in the main operating room or outpatient surgery center at Grady Memorial Hospital,
- Receive general anesthesia (standardized to sevoflurane for maintenance),
- Receive rocuronium for NMB,
- Receive neostigmine for NMB reversal,
- Achieve a TOF count of at least 3 twitches but not a TOF ratio of 0.9 fifteen minutes after neostigmine has been given, and
- Able and willing to provide informed consent.

Exclusion criteria:

Page 10 of 30 Version: 3 (10/14/2024)

- Pregnancy and/or lactating,
- BMI ≥ 40,
- Severe renal impairment, i.e. chronic kidney disease stages IV and V as defined by GFR < 30 ml/min/1.73 m² (21),
- Severe hepatic impairment, i.e. Child-Pugh score C⁵ (22, 23),
- Pre-existing neuromuscular disease,
- Anticipated need for postoperative intubation, and/or
- Known hypersensitivity reactions to rocuronium, neostigmine and/or sugammadex.

12. Population

We will not be including the following special populations:

- Adults unable to consent
- Individuals under the age of 18 years
- Pregnant women

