Review our Data and Safety Monitoring Questionnaire and insert the relevant monitoring table at the end of this section. Also upload the completed questionnaire in the "Basic Study Information" smartform section in eIRB, question #8, as a separate document.

| S | Select one of the following: | | |
|---|------------------------------|--|--|
| | ☐ Medium Complexity | | |
| | ☐ High Complexity Category A | | |

The study team will review the safety endpoints (nausea, vomiting, bradycardia, hypotension) on a monthly basis for the duration of the study. These safety endpoints are collected at each study visit and recorded in the study database. Patients are routinely assessed for these side effects in the PACU by their bedside nurse as well as the anesthesia resident who is responsible for discharging them from the PACU.

| | | Subgroup n=6 | | Total N=36 | |
|-------------|---|--------------|---------------------|------------|---------------------|
| Event | Assumed Probability Risk (upper end) | p<0.01 | Safety cut short if | p<0.01 | Safety cut short if |
| Nausea | | | | | |
| (high) | 0.25 | p=0.0046 | n≥5 | p=0.0086 | n≥16 |
| Vomiting | | | | | |
| (high) | 0.15 | p=0.0059 | n≥4 | p=0.0048 | n≥12 |
| Bradycardia | | | | | |
| (high) | 0.05 | p=0.0022 | n≥3 | p=0.0083 | n≥6 |
| Hypotension | | | | | |
| (high) | 0.15 | p=0.0059 | n≥4 | p=0.0048 | n≥12 |

Using the binomial equation (see below), we calculated the probability of seeing a set number of patients in each group, if the actual probability in the normal surgical population is at the level specified in the 'assumed probability' column.

For example, if the 'normal' probability of nausea is up to 25% (that is, the risk with treatment is the same as the risk under standard surgical conditions), then the chance of having 5 or more patients with nausea in any one treatment group is 0.0046, and the chance of having 16 or more patients with nausea in total is p=0.0048. Since this is unlikely, we will reject the null hypothesis, and conclude that the actual risk in our trial is actually higher than that. So if 5 or more patients report nausea in any one group or if 16 or more patients report nausea in total, this would trigger a suspension of the trial for further review.

Page 15 of 30 Version: 3 (10/14/2024)

$$P(X \ge x) = \sum_{x}^{N} {N \choose x} p^{x} (1-p)^{(N-x)}$$

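### Safety cut-offs are calibrated only for full enrolment, so the monthly review is unlikely to catch a moderate excess of events before about two thirds of patients are treated

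*Combined protocol and SAP*

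**What the plan says.** Section 21 schedules review of four safety endpoints by the study team "on a monthly basis for the duration of the study". Its table gives, for each event, an assumed risk and two cut-offs: one for a subgroup of 6 and one for the total of 36. The derivation is stated as "Using the binomial equation (see below), we calculated the probability of seeing a set number of patients in each group", taking the assumed risk as true and looking for a probability below 0.01.

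The two cut-offs are joined by an or. For nausea, the rule acts "if 5 or more patients report nausea in any one group or if 16 or more patients report nausea in total", and "this would trigger a suspension of the trial for further review". No row or column gives a limit for a partly enrolled trial or a partly filled group.

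On timing, Section 10 states "It is expected that 1 year would be required to enroll all study subjects", and Section 16 ends the study once the required number is reached. The monitoring table in Section 21 adds real-time data review and monthly adverse-event review by the principal investigator, neither with a numeric trigger.

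**The concern.** A monthly review is useful to the extent that it can act while patients remain to be treated. The stated counts are the ones that become improbable at 36 patients, or at 6 in a group. Earlier, the same counts are still required from fewer patients, so the rule is far stricter than p<0.01 at every review but the last. At 18 patients, for example, the total cut-offs need 16 of 18 with nausea (89%), 12 of 18 with vomiting or hypotension (67%) or 6 of 18 with bradycardia (33%), against assumed risks of 25%, 15% and 5%. An excess that the team would want to examine could then pass through most of the reviews without reaching a limit.

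**Working it through.** **Inputs (Section 21 table).** Nausea: "0.25 | p=0.0046 | n≥5 | p=0.0086 | n≥16". Vomiting and hypotension, identical rows: "0.15 | p=0.0059 | n≥4 | p=0.0048 | n≥12". Bradycardia: "0.05 | p=0.0022 | n≥3 | p=0.0083 | n≥6". In each row the order is assumed risk, tail probability and cut-off at n=6, tail probability and cut-off at N=36. From Section 10: one year of accrual, so 36/12 = 3 treated patients per monthly review if accrual is even (an assumption).

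**Step 1. Reproduce the plan's figures.** The formula is P(X ≥ r) = Σ from k=r to n of C(n,k) p^k (1−p)^(n−k). For nausea at n=6: 6 × 0.25^5 × 0.75 + 0.25^6 = 0.00439 + 0.00024 = 0.0046, as stated. All eight table values reproduce to four decimals, and each cut-off is the smallest count with a tail below 0.01. (The worked example below the table gives 0.0048 for 16 or more nausea events of 36. The table's 0.0086 is the value that reproduces.)

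**Step 2. Total rule alone, true risk doubled (50%, 30%, 10%).** Same formula, with the N=36 cut-off held fixed and n set to the number treated:

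| Event | n=18 | n=24 | n=30 | n=36 |
|---|---|---|---|---|
| Nausea (≥16) | 0.07% | 7.6% | 42.8% | 79.8% |
| Vomiting, hypotension (≥12) | 0.14% | 3.1% | 15.9% | 39.1% |
| Bradycardia (≥6) | 0.6% | 2.8% | 7.3% | 14.5% |

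At n=12, 16 nausea events are impossible, and vomiting or hypotension would need 12 of 12.

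**Step 3. Both rules together.** The per-group counts (5, 4, 3, 4) apply at the same reviews, so they must be included. Simulation: 6 patients per arm in random order, strata and blocks ignored, the same true risk in every arm, suspension when either rule is met.

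| Event | Risk | by 18 | by 24 | by 30 | by 36 |
|---|---|---|---|---|---|
| Nausea | doubled | 2% | 14% | 50% | 83% |
| Vomiting, hypotension | doubled | 3% | 11% | 27% | 50% |
| Bradycardia | doubled | 2% | 5% | 10% | 18% |
| Nausea | tripled | 23% | 90% | – | – |
| Vomiting, hypotension | tripled | 16% | 50% | – | – |
| Bradycardia | tripled | 7% | 18% | – | – |

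At doubled risk, the median point of triggering, among trials that trigger, is patient 29 to 30 of 36.

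**Step 4. Limits by number treated.** The smallest count with a tail below 0.01 at the assumed risk (tail in brackets, then the tail for one event fewer):

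| Event | n=12 | n=24 |
|---|---|---|
| Nausea | 8 (0.0028; 0.0143) | 12 (0.0072; 0.0213) |
| Vomiting, hypotension | 6 (0.0046; 0.0239) | 9 (0.0059; 0.0199) |
| Bradycardia | 4 (0.0022; 0.0196) | 5 (0.0060; 0.0298) |

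**Step 5. Effect of adding these to both existing rules** (same simulation):

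| Event | Fires by 24, doubled risk: now → with added limits | False alarm by 36, assumed risk: now → with added limits | False alarm with limits at about 12 monthly looks |
|---|---|---|---|
| Nausea | 14% → 60% | 3.3% → 3.7% | 4.9% |
| Vomiting, hypotension | 11% → 32% | 3.7% → 4.3% | 5.4% |
| Bradycardia | 5% → 10% | 2.0% → 2.3% | 3.4% |

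The false-alarm figures move by about 0.1 percentage point between simulation runs.

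**The case against.** The strongest reply is that the total cut-offs are only half of the rule. Three to five events in a single arm also suspend the trial, and that can happen well before patient 36. This stands, and it is why the figures above combine both rules. Quoting the total rule alone (about 8%, 3% and 3% by patient 24 at doubled risk) would understate the plan's protection. The per-group rule does not close the gap, because it too is set for a complete arm of 6. It also needs treatment allocation, while the review belongs to the study team of a double-blind trial and no unblinded reviewer is named.

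A reader might infer that the interim reviews have almost no chance of acting, or that the rule can fire only when nobody is left to protect. The documents do not support that. The cut-offs are plain counts joined by an or, so reaching one early counts. With nausea tripled, the trial would be suspended by patient 24 about 90% of the time. Even with nausea only doubled, it would be suspended by patient 30 about half the time. Nor is the count table the only safeguard: Section 21 also has ongoing and monthly review by the principal investigator and collection of serious adverse events, and Section 17 notes that the listed events are routinely watched for and treated in the PACU. These reviews have no numeric trigger, so they supplement a calibrated rule without replacing it.

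It is also fair to say that more looks cost more false alarms. Limits at every monthly review would add about 1.4 to 1.7 percentage points per event, against about 0.3 to 0.6 for two added looks.

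**Conclusion.** The point holds for a moderate excess. Section 21 plans monthly review but sets limits only for 36 patients and for 6 per group. At doubled risk, suspension for any one event has at most about a 3% chance by half enrolment and at most about 14% by two thirds. It does not hold for a large excess of nausea, and for vomiting or hypotension a tripled risk is caught by patient 24 about half the time. Bradycardia remains hard to detect early under either scheme, because the assumed risk is low and the trial is small.

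These results assume random order with 6 per arm, strata and blocks ignored, the same multiple of risk in all arms, and the table's assumed risks as the reference. The monthly-look figures also assume even accrual over one year. This is an inexpensive improvement to the monitoring rule. The existing cut-offs are correctly calculated for the sample sizes they name.

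**What to change.** Keep the existing per-group and total cut-offs. Add total-count limits to the Section 21 table at 12 and 24 treated patients, from the plan's own formula, assumed risks and p<0.01 threshold:

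- nausea 8 and 12
- vomiting 6 and 9
- bradycardia 4 and 5
- hypotension 6 and 9

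State in advance at which numbers treated the added limits apply, because the false-alarm rate depends on the number of looks. If the assumed risks are revised, recompute the limits.

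The cost is a larger table and the small rise in false alarms shown above. A crossing leads only to suspension for review. The added limits use pooled counts, so applying them needs no unblinding. The benefit is substantial for nausea, moderate for vomiting and hypotension, and small for bradycardia.

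### Section 21's nausea example gives 0.0048 for a total whose probability is 0.0086, and a one-group 0.0046 for a trigger that fires on any group (0.0275 over six).

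*Combined protocol and SAP*

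**What the plan says.** Section 21 of the combined protocol and SAP sets suspension cut-offs for nausea, vomiting, bradycardia and hypotension. For each event the table gives an assumed upper-end rate, a binomial tail and cut-off for a subgroup of 6, and the same for all 36 patients, with p<0.01 heading each set of tails. The nausea row reads "0.25 | p=0.0046 | n≥5 | p=0.0086 | n≥16". The basis is described as "we calculated the probability of seeing a set number of patients in each group", and a single binomial tail formula follows.

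The worked example covers nausea only. It takes the null to be that the normal "probability of nausea is up to 25" per cent. It then says that "the chance of having 5 or more patients with nausea in any one treatment group is 0.0046", and that "the chance of having 16 or more patients with nausea in total is p=0.0048". It continues: "Since this is unlikely, we will reject the null hypothesis", and infers that the trial's actual risk is higher. The rule follows: "So if 5 or more patients report nausea in any one group or if 16 or more patients report nausea in total", the trial is suspended pending review.

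**The concern.** Two things do not fit. First, the total-sample probability in the prose (0.0048) differs from the one in the nausea row of the table (0.0086), although the cut-off of 16 and the rate of 25% are the same. Second, the group probability of 0.0046 comes from a single group of 6, while the rule it supports acts on whichever group reaches 5. With six groups there are six chances to trigger, so the probability that justifies the rule should be larger than the one-group value.

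What is at stake is how a suspension is interpreted. Section 21 classes the trial as more than minimal risk, and these are its only numerical suspension thresholds. The text argues directly from the size of the probability to a conclusion about risk. If the probability is understated, whoever reviews a suspension will give the trigger more weight as evidence of harm than it has.

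**Working it through.** **Inputs.** Assumed nausea rate 0.25, group size 6, total 36, cut-offs 5 and 16 (section 21 table and example). Six groups, namely five sugammadex doses and placebo (section 5), with six patients in each (section 7, Table 1). Vomiting and hypotension: rate 0.15, cut-offs 4 and 12. Bradycardia: rate 0.05, cut-offs 3 and 6 (section 21 table). Patients are taken as independent, with the same rate in every group.

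**Step 1: reproduce the table.** With the plan's own upper-tail formula, for one group:

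P(X≥5 | 6, 0.25) = 6 × 0.25⁵ × 0.75 + 0.25⁶ = 0.004395 + 0.000244 = 0.00464.

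This matches the table's 0.0046. The other subgroup values also match: P(X≥4 | 6, 0.15) = 0.00589 and P(X≥3 | 6, 0.05) = 0.00223. For the totals, P(X≥16 | 36, 0.25) = 0.00858, P(X≥12 | 36, 0.15) = 0.00477 and P(X≥6 | 36, 0.05) = 0.00834. All eight table entries reproduce to four decimals. One count below each cut-off gives a tail above 0.01 (groups 0.0376, 0.0473, 0.0328; totals 0.0209, 0.0137, 0.0324), so every cut-off is the smallest that meets p<0.01 for its own cell.

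**Step 2: the total in the prose.** The nausea total is 0.0086, not 0.0048. Neighbouring cut-offs do not give 0.0048 either (15 or more: 0.0209; 17 or more: 0.0032). It is the rounded value of P(X≥12 | 36, 0.15) = 0.00477, which is the vomiting and hypotension entry.

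**Step 3: the group trigger.** For k independent groups, P(at least one reaches the cut-off) = 1 − (1 − p)^k. For nausea:

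- six groups: 1 − (1 − 0.004639)⁶ = 0.0275
- five sugammadex groups: 1 − (1 − 0.004639)⁵ = 0.0230

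As odds, 1/0.004639 is about 1 in 216, 1/0.0275 about 1 in 36 and 1/0.0230 about 1 in 44. For the total, 1/0.0048 is about 1 in 210 and 1/0.00858 about 1 in 117.

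**Step 4: all four events.** The group-or-total column combines both parts of the rule. It convolves six binomials truncated below the group cut-off, sums the probability of totals below the total cut-off, and subtracts the result from 1.

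| Event (rate) | One group | Any of six | Any of five | Total of 36 | Any of six, or total |
|---|---|---|---|---|---|
| Nausea (0.25) | 0.0046 | 0.0275 | 0.0230 | 0.0086 | 0.0332 |
| Vomiting (0.15) | 0.0059 | 0.0348 | 0.0291 | 0.0048 | 0.0372 |
| Bradycardia (0.05) | 0.0022 | 0.0133 | 0.0111 | 0.0083 | 0.0191 |
| Hypotension (0.15) | 0.0059 | 0.0348 | 0.0291 | 0.0048 | 0.0372 |

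The monthly reviews add nothing to these figures: counts only accumulate and the cut-offs are fixed, so a trigger at any look is also present in the final counts.

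**The case against.** The best defence concerns 0.0046. The table is headed for a subgroup of 6, the text says the calculation was made for each group, and the formula is a single binomial. On that basis any one group could mean a given group, and 0.0046 is the right number for that quantity. This stands as a defence of the table. It does not rescue the worked example, because the trigger sentence uses nearly the same words for a rule that acts on whichever group reaches 5. The probability used to justify that rule has to describe that rule.

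A second defence is that nothing operational changes. That is correct: the cut-offs are the same in table and text, both 0.0048 and 0.0086 are below 0.01, and the consequence is a suspension for review rather than termination. The effect is confined to what a trigger is taken to show.

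Three stronger readings are tempting and are not supported:

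- A reader might infer that the table or its cut-offs are wrong because 0.0275 exceeds 0.01. The p<0.01 criterion is applied cell by cell, and every cell meets it.
- A reader might infer that the plan breaks a promised limit on false suspensions across the whole rule. It states no such rate and sets no such limit, so there is nothing for the any-group figures to contradict.
- A reader might say that the plan misstates the probabilities for all four events. The prose example covers nausea alone; the other three appear only in the table, which is correct on its stated per-group basis.

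**Conclusion.** The point holds for the worked example. The 0.0048 is a plain internal contradiction: table and exact calculation agree on 0.0086. The 0.0046 is a one-group probability attached to an any-group trigger whose probability at the assumed rate is 0.0275, or 0.0230 if placebo is not counted. Either value is five to six times the figure given, so a nausea trigger in some group is not p<0.01 evidence of excess risk, as the example implies.

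The any-group figures assume independent patients, a common rate in all groups, full groups of 6, and the upper-end rates in the table. The plan's null covers rates up to 25%, so the true chance may be lower. For illustration, at 23% (the lower end for nausea in section 17) the group-or-total probability falls from 0.0332 to 0.0210. The errors affect interpretation of a suspension, not when the rule fires.

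**What to change.** In the section 21 worked example, change 0.0048 to 0.0086. Label 0.0046 and the other subgroup values as probabilities for a single specified group. Beside them, state the any-of-six-groups probabilities at the assumed upper-end rates: nausea 0.0275, vomiting 0.0348, bradycardia 0.0133, hypotension 0.0348. If placebo is not counted in the group rule, use the five-group values instead (0.0230, 0.0291, 0.0111, 0.0291). The group-or-total values (0.0332, 0.0372, 0.0191, 0.0372, with all six groups counted) can be added if wanted. Reword the inference so that a trigger in some group is not presented as p<0.01 evidence.

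Keep the table values and the cut-offs. The cost is a text edit with no new data. The example will then describe a trigger as weaker evidence than it does now.
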